#### 11.1.5 STUDY DISCONTINUATION AND CLOSURE

This study may be temporarily suspended or prematurely terminated if there is sufficient reasonable cause. Written notification, documenting the reason for study suspension or termination, will be provided by the suspending or terminating party to study participants, funding agency, and regulatory authorities. If the study is prematurely terminated or suspended, the Principal Investigator (PI) will promptly inform study participants, the Institutional Review Board (IRB), and sponsor/funding agency and will provide the reason(s) for the termination or suspension. Study participants will be contacted, as applicable, and be informed of changes to study visit schedule.

Circumstances that may warrant termination or suspension include, but are not limited to:

- Determination of unexpected, significant, or unacceptable risk to participants
- Insufficient compliance of study staff to the protocol (i.e., significant protocol violations)
- Data that are not sufficiently complete and/or evaluable

The study may resume once concerns about safety, protocol compliance, and data quality are addressed, and satisfy the funding agency, sponsor, IRB, or other relevant regulatory or oversight bodies (OHRP, DSMB).

---

#### 11.1.6 CONFIDENTIALITY AND PRIVACY

Participant confidentiality and privacy is strictly held in trust by the participating investigators, staff, and the funding agency. This confidentiality is extended to the data being collected as part of this study. Data that could be used to identify a specific study participant will be held in strict confidence within the research team. No personally identifiable information from the study will be released to any unauthorized third party without prior written approval of the funding agency. All research activities will be conducted in as private a setting as possible.

Authorized representatives of the funding agency, or representatives of the Institutional Review Board (IRB) may inspect all documents and records required to be maintained by the investigator

The study participant's contact information will be securely stored for internal use during the study. At the end of the study, all records will continue to be kept in a secure location for as long a period as dictated by the reviewing IRB, Institutional policies, or sponsor/funding agency requirements.

Study participant research data, which is for purposes of statistical analysis and scientific reporting, will be transmitted to and stored in a secure server maintained by the University of Minnesota Academic Health Center Information Exchange or by University of Minnesota Information Technology office; the storage and access space for the data will be HIPAA compliant and include Includes encryption, activity logging, Duo Two-Factor Authentication, and access controls such as view-only access.. This will not include the participant's contact or identifying information. Rather, individual participants and their research data will be identified by a unique study identification number. The study data entry and study management systems used by research staff will be secured and password protected. At the end of the study, all study databases will be de-identified and archived at the Data Repository for the University of Minnesota (DRUM).

#### Measures Taken to Ensure Confidentiality of Data Shared per the NIH Data Sharing Policies

It is NIH policy that the results and accomplishments of the activities that it funds should be made available to the public (see <https://grants.nih.gov/policy/sharing.htm>). The PI will ensure all mechanisms used to share data will include proper plans and safeguards for the protection of privacy, confidentiality, and security for data dissemination and reuse (e.g., all data will be thoroughly de-identified and will not be traceable to a specific study participant). Plans for archiving and long-term preservation of the data will be implemented, as appropriate.

---

##### 11.1.6.1 CERTIFICATE OF CONFIDENTIALITY

To further protect the privacy of study participants, the Secretary, Health and Human Services (HHS), has issued a Certificate of Confidentiality (CoC) to all researchers

engaged in biomedical, behavioral, clinical or other human subjects research funded wholly or in part by the federal government. Recipients of NIH funding for human subjects research are required to protect identifiable research information from forced disclosure per the terms of the NIH Policy (see <https://humansubjects.nih.gov/coc/index>). As set forth in 45 CFR Part 75.303(a) and NIHGPS Chapter 8.3, recipients conducting NIH-supported research covered by this Policy are required to establish and maintain effective internal controls (e.g., policies and procedures) that provide reasonable assurance that the award is managed in compliance with Federal statutes, regulations, and the terms and conditions of award. It is the NIH policy that investigators and others who have access to research records will not disclose identifying information except when the participant consents or in certain instances when federal, state, or local law or regulation requires disclosure. NIH expects investigators to inform research participants of the protections and the limits to protections provided by a Certificate issued by this Policy.

---

#### 11.1.7 FUTURE USE OF STORED SPECIMENS AND DATA

Data collected for this study will be analyzed and stored in a secure server maintained by the University of Minnesota Academic Health Center Information Exchange or by University of Minnesota Information Technology office; the storage and access space for the data will be HIPAA compliant and include encryption, activity logging, Duo Two-Factor Authentication, and access controls such as view-only access. After the study is completed, the de-identified, archived data will be transmitted to and stored at the Data Repository for the University of Minnesota (DRUM), for use by other researchers including those outside of the study. Permission to transmit data to the DRUM will be included in the informed consent. Access to study data will be provided through the DRUM.

---

#### 11.1.9 SAFETY OVERSIGHT - DSMB

Safety oversight will be under the direction of a Data and Safety Monitoring Board (DSMB) composed of individuals with the appropriate expertise, including trial conduct and research data storage and use. Members of the SMC will be independent from the study conduct and free of conflict of interest. The SMC will meet at least semiannually to assess safety and efficacy data from each arm of the study. The SMC will operate under the rules of an approved charter that will be written and reviewed at the organizational meeting of the DSMB. At this time, each data element that the SMC needs to assess will be clearly defined. The DSMB will provide its input to National Institutes of Health staff.

---

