## 2.3 SCHEDULE OF ACTIVITIES

	Pre-consent: Health system sends mailing based on eligibility	Consent (by research coordinators )	Visit 1 Day 1	Visit 2 Day 90 +/- 15 days	Unscheduled Visit
EMR Review Eligibility	X				
Informed Consent		X			
Demographics			X		
Outcome Evaluation					
Randomization			X		
Control & Experimental Interventions – GogyUp Reader app.			X	X	
Outcomes assessments			X	X	
Adverse Events Reporting			X	X	X

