## 8 STUDY INTERVENTION/EXPERIMENTAL MANIPULATION DISCONTINUATION AND PARTICIPANT DISCONTINUATION/WITHDRAWAL

### 8.1 DISCONTINUATION OF STUDY INTERVENTION/EXPERIMENTAL MANIPULATION

Other than participant withdrawal (self-decided for any reason), we do not have any specific circumstances that would lead us to discontinue participants from the study. Because the intervention is a mobile app that participants will use on a self-directed, as-needed basis, it will be available to participants regardless of moves, or other changes in circumstance. In the case of adverse events, we would not revoke a participants' access to the app, but it could mean issues with loss to follow up, which we will address below.

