## 9.2 SAFETY ASSESSMENTS

N/A

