#### 9.4.2 UNANTICIPATED PROBLEMS REPORTING

The investigator will report unanticipated problems (UPs) to the reviewing Institutional Review Board (IRB) and to the lead research co-principal investigator (Co-PI [name]). The UP report will include the following information:

- Protocol identifying information: protocol title and number, PI's name, and the IRB project number
- A detailed description of the event, incident, experience, or outcome
- An explanation of the basis for determining that the event, incident, experience, or outcome represents an UP
- A description of any changes to the protocol or other corrective actions that have been taken or are proposed in response to the UP

To satisfy the requirement for prompt reporting, UPs will be reported using the following timeline:

- UPs that are serious adverse events (SAEs) will be reported to the IRB and to the funding agency within 24 hours of the investigator becoming aware of the event
- Any other UP will be reported to the IRB and to the funding agency within 36 hours of the investigator becoming aware of the problem
- All UPs should be reported to appropriate institutional officials (as required by an institution's written reporting procedures), the supporting agency head (or designee), and the Office for Human Research Protections (OHRP) within 7 days of the IRB's receipt of the report of the problem from the investigator

---

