#### 10.4.4 SAFETY ANALYSES

N/A

---

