### 15.8.2 SCRIPT FOR FOLLOW-UP ASSESSMENT - PHONE OR ONLINE MEETING

If the follow-up assessment appointment is schedule as a phone meeting:

*Hello. This is [YOUR NAME] FROM GogyUp. Is [NAME OF PARTICIPANT] available?*

*Wait for confirmation that you are speaking with the participant.*

*I am calling to take our GogyUp / University of Minnesota Type 2 Diabetes survey with you. Is this still a good time?*

*Wait for confirmation that participant is ready, then explain why we're administering the assessment.*

*Great! Before we begin, do you have any questions for me about the survey or the study?*

Answer questions that the participant has, referring to the Online Disclosure Document as necessary.

Display the JotForm assessment.

Administer the HLQ and PDSMS according to directions posted on the JotForm site.

For participants in the intervention group, administer the User Experience Questions after the HLQ and PDSMS. Record participant scores using the online form. If the participant asks additional questions or provides additional feedback, record in the comments area of the participant's database record.

---

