15.9.7 FOLLOW-UP: USER EXPERIENCE QUESTIONS (INTERVENTION GROUP ONLY): OPEN ENDED

- 1) Describe what you like most about the app and why.
- 2) Describe what you found frustrating and why.
- 3) Describe what your primary motivation might be for downloading the app.
- 4) What features did you frequently use on the app?
- 5) Under what circumstances would you continue to use the app?

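### Adverse event reporting is scheduled and the board is to assess safety by arm, but no visible assessment script or form asks either arm about adverse events

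*Combined protocol and SAP*

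**What the plan says.** Several parts of the protocol assume that adverse events will be known.

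- The Schedule of Activities (2.3) has a row "Adverse Events Reporting", marked at Visit 1, Visit 2 and the unscheduled visit.
- Section 8.1 says that an adverse event would not end access to the app, "but it could mean issues with loss to follow up, which we will address below".
- Section 9.4.2 sets a clock: "UPs that are serious adverse events (SAEs) will be reported to the IRB and to the funding agency within 24 hours". The time is counted from when the investigator learns of the event.
- Section 11.1.9 says of the board: "The SMC will meet at least semiannually to assess safety and efficacy data from each arm of the study". It leaves the list of data elements to a charter still to be written.

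The operative sections do not follow through. "9.2 SAFETY ASSESSMENTS" and "10.4.4 SAFETY ANALYSES" are both marked not applicable. Section 9.3, on adverse and serious adverse events, describes only a breach of data. Section 11.1.10 says that the team has no clinical information to monitor.

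The baseline script (15.6.2) gives the HLQ and demographic items. The follow-up notes and script (15.8, 15.8.2) give the HLQ and PDSMS to both arms, and for the app arm tell staff to "administer the User Experience Questions after the HLQ and PDSMS". Those app-only items (15.9.6, 15.9.7) include "Describe what you found frustrating and why".

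**The concern.** A board that is asked to assess safety by arm needs data collected the same way in both arms. Followed as written, the plan collects none systematically. Staff cannot both report adverse events at the scheduled visits and treat safety assessment as not applicable. A charter can name the data elements that the board wants, but it cannot supply data that no visit collects.

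Two things are at stake. First, an absence of reports could be read as an absence of events, although nobody was asked. Second, and of less weight, the reports that do come in arise from unequal contact. App-arm participants have app technical support (7.2.1), a coordinator call if the account shows no activity at the start (11.1.4, step 7), and usability questions at follow-up. A difference in volunteered reports could therefore reflect contact rather than events.

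**Working it through.** The plan gives no safety figure to reproduce. The check is a comparison of sections, with two small calculations for scale.

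**1. What is promised against what is collected**

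| Promise | Where | Procedure found |
|---|---|---|
| Adverse event reporting at Visit 1 | 2.3 | 15.6.2 and 15.9.4: HLQ and demographics, no event item |
| Adverse event reporting at Visit 2 | 2.3 | 15.8.2 and 15.9: HLQ and PDSMS, plus app-only usability items, no event item |
| Adverse event reporting at unscheduled visits | 2.3 | No procedure for such a visit |
| Reporting clock from investigator awareness | 9.4.2 | No step that sends a reported event to the investigator |
| Safety data from each arm | 11.1.9 | 9.2 and 10.4.4 not applicable; 9.3 data breach only |

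**2. Other sources**

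- Clinical records: ruled out by 11.1.10.
- Comments field: 15.8.2 has staff record extra questions or feedback from any participant. This is open to both arms, but it is free text and does not ask about events.
- Questions to investigators: 15.6.2 forwards baseline questions that the disclosure document cannot answer. The follow-up script has no such instruction.
- Participant-initiated contact: both welcome letters (15.7.1, 15.7.4) give the coordinator's details, and both send health questions to the participant's own doctor or clinic.
- Withdrawal reasons: recorded on an electronic case report form (8.2). Participants who cannot be reached are coded only as lost to follow-up (8.3).

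Every remaining route is passive.

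**3. What asking would give**

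If n participants all answer and none reports an event, the one-sided 95% upper bound on the event rate is 1 − 0.05^(1/n). The values of n are the planned numbers per arm in 10.2.

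- n = 80: 1 − 0.05^(1/80) = 3.7%
- n = 60: 1 − 0.05^(1/60) = 4.9%

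Both assume that everyone answers; with fewer answers the bound is wider. If nobody is asked, zero reports gives no bound.

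**4. What unequal reporting could do**

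The documents give no reporting probabilities, so these are assumptions. Take the same true event rate of 10% in both arms, 80 per arm, and a probability of 0.8 that an app-arm event is recorded. Expected recorded events are 80 × 0.10 × the probability of recording.

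| Probability, app v control | Expected events, app v control | Apparent ratio |
|---|---|---|
| 0.8 v 0.8 | 6.4 v 6.4 | 1.0 |
| 0.8 v 0.4 | 6.4 v 3.2 | 2.0 |
| 0.8 v 0.2 | 6.4 v 1.6 | 4.0 |

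The ratio depends only on the two recording probabilities. This shows the mechanism; it does not estimate what would happen in this trial.

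**The case against.** The best case for leaving the plan alone is that the intervention is a self-directed reading app over public CDC fact sheets, confidentiality is the only risk anticipated (3.3.1, 9.3), and safety is neither an objective nor an endpoint (section 4). Breaches are found through data systems, not by asking participants. The board's expertise, as described in 11.1.9, fits that narrow scope, and its charter may define its data accordingly. Section 11.2.2 cites a Manual of Procedures that was not available for review, and the consent text was removed from the review copy; either may tell participants how to report a problem.

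Much of this stands as a limit on weight, and it is why the finding is confined to visible assessment scripts and forms. It does not remove the contradiction. If the scope is confidentiality only, the adverse event row in 2.3 and the by-arm safety task in 11.1.9 are wrong as written. A reporting contact in the consent form would be one more passive route.

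Four stronger readings are tempting, and the documents do not support them.

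- *Only the app arm is asked about problems.* The app-only items concern the usability of the app, not health. Both arms are asked whether they have questions, and both can have feedback recorded. The inactivity call is an access check at the start.
- *Events behind drop-out would be invisible.* Section 8.2 records reasons for withdrawal in either arm. The gap is for those who cannot be reached.
- *The 24-hour clock could never start.* Passive routes to the investigators exist, such as the forwarding instruction in 15.6.2. What is missing is a defined step for events.
- *The board would have nothing to compare.* HLQ and PDSMS data by arm will exist. The gap is in safety data.

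**Conclusion.** The point holds as an inconsistency between sections with a practical consequence: followed as written, the plan gives the board no systematically collected safety data from either arm. The unequal contact is secondary. It makes volunteered reports doubtful for comparison, by an amount that the documents do not allow anyone to estimate.

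The change is worth making because it is cheap, but its weight is modest. No planned efficacy result is affected. The 3.7% and 4.9% bounds only illustrate what full answering with zero events would show. The conclusion assumes that the unseen manual and consent text contain no structured adverse event question put to both arms. If they do, the remaining work is to cite it in 9.2 and 10.4.4.

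**What to change.** Add one identical, neutrally worded open question to the Visit 2 script for both arms, after the HLQ and PDSMS and before the app-only items, so that outcome measurement is not disturbed. It should ask about any new health problem or other problem since joining the study. Record the participant's view of whether it relates to the study as a separate field, so that events are not filtered by that view. Ask the same question of withdrawing participants who can be reached.

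State that the coordinator promptly forwards any positive answer to a designated investigator or safety contact who has no part in the blinded analysis, so that the clocks in 9.4.2 can start. Masking the report to arm should not be relied on, because an answer that mentions the app reveals the arm.

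Replace the not-applicable entries in 9.2 and 10.4.4 with this collection and a descriptive count by arm for the board. List spontaneous reports separately. Align the Visit 1 and unscheduled-visit marks in 2.3 with what will actually be collected.

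Alternatively, if the sponsor intends a confidentiality-only scope, reconcile 2.3, 9.2, 9.3, 10.4.4 and 11.1.9 to say so, and make no by-arm safety statement.

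The cost of the first option is about one minute per follow-up call, one form field, one table and a minor amendment. The question will not reach participants who are lost without contact.

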#### 11.1.10 CLINICAL MONITORING

Despite being a randomized controlled trial, this study will take place outside of the clinical environment and examines an intervention that is used outside of any clinical site. The research team also does not have access to clinical information for monitoring and the research team has no specific clinical role or clinical access with the possible exception of [name] in general terms as a practicing clinician-researcher.

---

#### 11.1.11 QUALITY ASSURANCE AND QUALITY CONTROL

The investigator team will perform internal quality management of study conduct, data collection, documentation and completion.

Quality control (QC) procedures will be implemented as follows:

**Informed consent** --- Study staff will review both the documentation of the consenting process as well as a percentage of the completed consent. This review will evaluate compliance with GCP, accuracy, and completeness.

**Source documents and the electronic data** --- Data will be initially captured on source documents (see **Section 11.2, Data Handling and Record Keeping**) and will ultimately be entered into the study database. To ensure accuracy, study staff will compare a random sample of source data documents against the database, targeting key data points in that review.

**Intervention Fidelity** — Consistent delivery of the study interventions will be monitored throughout the intervention phase of the study. Procedures for ensuring fidelity of intervention delivery are described in **Section 7.2.1, Interventionist Training and Tracking**.

**Protocol Deviations** – The study team will review protocol deviations on an ongoing basis and will implement corrective actions when the quantity or nature of deviations are deemed to be at a level of concern.

Should independent monitoring become necessary, the PI will provide direct access to all trial related sites, source data/documents, and reports for the purpose of monitoring and auditing by the sponsor/funding agency, and inspection by local and regulatory authorities.

## 11.2 DATA HANDLING AND RECORD KEEPING

### 11.2.1 DATA COLLECTION AND MANAGEMENT RESPONSIBILITIES

Data collection will be the responsibility of the study staff under the supervision of the principal investigators. The investigators will be responsible for ensuring the accuracy, completeness, legibility, and timeliness of the data reported.

All source documents will be completed electronically with timestamped activity. End-user data generated in GogyUp Reader will be stored internally by GogyUp by study id and merged with other participant data for exploratory analysis of “adherence” and literacy. Data recorded in the electronic case report form (eCRF) derived from source documents will be consistent with the data recorded on the source documents.

Source document data will be exported from JotForm HIPAA compliant webforms via CSV and be entered into REDCap, a 21 CFR Part 11-compliant data capture system available to the study team through the University of Minnesota’s Clinical and Translational Sciences Institute. The data system includes password protection and internal quality checks, such as automatic range checks, to identify data that appear inconsistent, incomplete, or inaccurate. Clinical data will be entered directly from the source documents.

#### 11.2.1.1 STUDY RECORDS RETENTION

Any source document records containing HIPAA PHI will be maintained for a minimum of 6 years after the end of the study in REDCap (follow-up assessments complete or lost to follow up met for all participants) AND Federal Financial Report (FFR) submission. Other records will be maintained for a minimum of 3 years.

